Screening: A complete medical history will be taken. Patients will be specifically asked about renal, hepatic or adrenal abnormalities and pregnancy (women of child bearing potential only). In keeping with current standard of care, no routine blood work will be done, unless it is deemed necessary by the investigator. Patients will be randomly assigned to IL TAC 2.5mg/ml, IL TAC 5mg/ml or IL TAC 10mg/ml or intralesional saline in a 1:1:1:1 ratio based on a computer generated randomization list. The list will be generated prior to study initiation. Based on the randomization list, patients will be assigned to treatment vs. placebo based on the order in which they are enrolled. The assignment will be made by study personnel not involved in making clinical assessments or evaluations. The patient and the assessing physicians will remain blinded to the treatment assignment for the duration of the study. Baseline assessments of disease severity will be done, including SALT, Physician global assessment (PGA), patient global assessment and patient quality of life assessment. Patients will have study medication injected once per month by the study physician in accordance with current standard of care clinical practice. Per current clinical practice, attempts will be made to treat all areas of hair loss due to AA, however (also in accordance with current standard of care in clinical practice) the dose of intralesional triamcinolone injected will be limited to a maximum of 30mg per month(16, 4). Therefore, patients being

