treated with IL TAC 2.5mg/ml will have up to a maximum of 12ml of drug injected, those treated with IL TAC 5mg/ml will have up to a maximum of 6ml of drug injected, while patients being treated with IL TAC 10mg/ml will receive a maximum of up to 3ml of drug injected. In an attempt to maintain the blinding of the evaluating investigator, patients receiving saline placebo, will have either 3ml, 6ml, or 12ml drawn up at the discretion of the unblinded study staff member preparing the medication. When possible, an unblinded physician investigator will perform study medication injections. If the blinded evaluating investigator must perform injections, the syringes will be covered such that the solution contained within is not visible. The entire syringe will be covered. After injections are completed, the unblended study team member will collect the used and unused syringes and calculate the total volume injected. This amount will be recorded and concealed to maintain integrity.

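### When the blinded evaluator also gives the injections, a covered syringe does not hide approximate volume, which can narrow the assignment to one IL TAC strength or saline

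*Combined protocol and SAP*

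**What the plan says.** All of the following is in the Combined protocol and SAP.

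- **Assessor blinding.** Study procedures (Screening): "The patient and the assessing physicians will remain blinded to the treatment assignment for the duration of the study".
- **Volume ceilings.** The same paragraph states that "the dose of intralesional triamcinolone injected will be limited to a maximum of 30mg per month". It derives a ceiling for each strength. At the lowest strength, patients "treated with IL TAC 2.5mg/ml will have up to a maximum of 12ml of drug injected". The corresponding limits are 6 ml at 5 mg/ml and 3 ml at 10 mg/ml.
- **Saline volume.** To protect the evaluator's blind, saline patients "will have either 3ml, 6ml, or 12ml drawn up at the discretion of the unblinded study staff member preparing the medication". The parallel text under Human Subjects Involvement, Characteristics, and Design also ties this volume to the extent of hair loss. The Screening text does not.
- **Who injects.** An unblinded physician injects when possible. Otherwise: "If the blinded evaluating investigator must perform injections, the syringes will be covered such that the solution contained within is not visible". The text adds that the whole syringe is covered.
- **Concealment of volume.** Unblinded staff collect used and unused syringes afterwards and work out the total. Of that total the plan says: "This amount will be recorded and concealed to maintain integrity".
- **Scoring.** The visit lists have the physician score SALT and PGA at baseline, at every four-weekly visit and at week 24. The primary endpoint is at least 50% SALT regrowth at week 24.

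**The concern.** The plan treats injected volume as information that could break the blind. It varies the saline volume for the evaluator's sake and conceals the total afterwards. The exception then gives the evaluator the one task in which volume is directly experienced. The only stated protection is the cover.

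Nothing limits how often the exception may be used, records when it was used, or stops the same person from scoring that patient later. SALT is a visual estimate by a clinician, and the primary endpoint cuts it at 50%. Two analyses could be affected: the four-group comparison of response, and the head-to-head comparison of the three strengths that the Data Analysis Plan adds if the four-group test is significant.

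**Working it through.** **Inputs**

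- Monthly ceiling 30 mg and strengths 2.5, 5 and 10 mg/ml (Study procedures, Screening).
- Allocation 1:1:1:1 (same section).
- About 0.1 ml per injection site (Clinical experience with IL TAC for AA). This describes general practice and is not a trial instruction.
- *q*, the share of saline patients drawn up to a given volume. The documents do not give it, so a range is shown.

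**Step 1: reproduce the ceilings.** Volume = 30 mg / strength: 30/2.5 = 12 ml, 30/5 = 6 ml, 30/10 = 3 ml. All three match the protocol.

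**Step 2: what the injector can perceive.** Number of sites = volume / 0.1 ml: 12/0.1 = 120, 6/0.1 = 60, 3/0.1 = 30. A four-fold spread (120/30) can be noticed without seeing the liquid or the graduations. So can the number of syringes used, and a supply that ends with areas still untreated.

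**Step 3: arms compatible with an injected total**

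| Injected total | Compatible arms |
|---|---|
| up to 3 ml | all four |
| above 3, up to 6 ml | 5 mg/ml, 2.5 mg/ml, saline |
| above 6, up to 12 ml | 2.5 mg/ml, saline |

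A supply that visibly runs out tells more than the total alone. If active drug is drawn to its ceiling, a supply ending at 3 ml leaves 10 mg/ml or saline, one ending at 6 ml leaves 5 mg/ml or saline, and one ending at 12 ml leaves 2.5 mg/ml or saline.

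**Step 4: how far a ceiling supply shifts the probabilities.** Assume every active patient is drawn to the ceiling. Then P(matching strength | supply V) = (1/4) / (1/4 + q/4) = 1/(1 + q).

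| q at that volume | P(matching strength) | P(saline) |
|---|---|---|
| 0 | 1.00 | 0.00 |
| 0.1 | 0.91 | 0.09 |
| 1/3 | 0.75 | 0.25 |
| 0.5 | 0.67 | 0.33 |
| 1 | 0.50 | 0.50 |

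Before anything is seen, P(any active arm) = 3/4 = 0.75 and each strength has 0.25.

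**Step 5: the two descriptions of the saline volume**

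- *Equal thirds (q = 1/3).* The 0.75 equals the prior for active drug, so volume says nothing about active versus saline. It does separate the strengths: the matching one goes from 0.25 to 0.75 and the other two to zero.
- *Volume following extent of loss.* In a patient with extensive loss, few saline supplies would be 3 ml. At q = 0.1 the probability of active drug is 0.91, above the 0.75 prior, so a short supply points away from saline. If most such saline patients get 12 ml (q towards 1), a 12 ml supply lowers it towards 0.50.

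**Step 6: the provisions side by side.** Injections are given at baseline and weeks 4, 8, 12, 16 and 20, so the impression can form at up to six visits. SALT and PGA are scored at weeks 4 to 24. Concealing the calculated total protects an evaluator who did not inject. It does not protect one who did, and the assessor-blinding rule makes no exception for that person.

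**The case against.** The case against is substantial and much of it stands.

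- The evaluator is not the default injector.
- The whole syringe is covered, and the exact total is worked out later by unblinded staff. The evaluator infers an approximate volume and is never told one.
- Unused syringes are also collected, so the supply need not visibly run out. The documents give neither syringe size and number nor a statement that active drug is always drawn to its ceiling. The Baseline to Week 48 text lets the investigator choose areas on clinical grounds, so stopping early has other explanations.
- The plan assumes about 50% response on active drug whatever the strength, so no direction of bias between strengths can be predicted.
- Standardised photographs, in views consistent with SALT, are taken at baseline and at each visit to week 24.

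These points rule out four stronger readings that a reader might infer:

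1. *Volume identifies the strength.* It does not. Saline is drawn to the same three volumes, and a total of 3 ml or less fits every arm.
2. *A short supply in extensive loss proves active drug.* That needs q = 0. Even the text that mentions extent leaves the volume to staff discretion.
3. *The effect could never be examined.* The photographs allow a partial check, although the plan specifies no independent blinded reading of them.
4. *Two patients in an arm of 17, or 2/17 = 11.8 points, is the likely bias.* That is the arithmetic of arm size and applies to any scoring error. It is not an estimate of effect.

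What the objection does not remove is that the injector sees and performs every injection, and no text keeps that person from scoring the patient afterwards.

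**Conclusion.** The concern holds in a limited form. When the exception is used, the evaluator can infer approximate volume, and this can narrow the assignment to one strength or saline, mainly in patients with extensive hair loss. That conflicts with the concealment of volume and with the assessor-blinding rule.

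The strength comparison is exposed under either description of the saline volume. The active-versus-saline contrast is exposed only if saline volumes are unevenly split, as they would be if they followed extent of loss.

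The probabilities assume that active patients are drawn to the ceiling and that the injector notices the supply ending. The site counts assume about 0.1 ml per site. The size of any bias cannot be given: the documents state neither how often the exception would be used nor what share of patients have enough hair loss for the ceilings to bind. The change is still worth making because the primary endpoint is clinician-scored and the cost is low.

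**What to change.** In Study procedures (Screening), after the exception:

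1. State that, where another blinded assessing physician already on the study team is available, an investigator who has injected a patient does not score that patient's SALT or PGA at later visits through week 24.
2. Record injector and scorer at every visit.
3. Report by arm how many patients were scored by someone who had injected them.
4. Keep the intention-to-treat analysis as primary. Pre-specify a sensitivity analysis of week-24 response restricted to patients never scored by their injector.

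The first rule is conditional because an absolute ban could force a site to add a blinded assessor. Where no substitute is available, items 2 to 4 at least make the overlap visible.

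**Cost.** Protocol wording, two case report form fields and one analysis. Visit staffing becomes less flexible. A change of scorer within a patient adds some inter-rater variation to percent change in SALT. With 17 per arm the sensitivity analysis will be small and imprecise, and its subset is defined by staffing after randomisation, so it can only support the primary result. No dose, volume or treatment rule changes.

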“coincidentally with the triamcinolone therapy”. No mention is made of randomization or blinding. At follow-up satisfactory regrowth was defined as “the presence of predominantly pigmented terminal hair at the injection sites in significant quantity”. “Significant quantity” was not further described. Regrowth was noted to occur in tufts corresponding to the injection sites within 4 to 6 weeks, and was often accompanied by evidence of minimal, transient skin atrophy. When divided into limited alopecia vs alopecia totalis/universalis, 71% of patients with limited AA had regrowth at 12 weeks vs 28% of patients with alopecia totalis/universalis. Seven percent of patients treated with saline had regrowth at 12 weeks, however the authors attributed the incidence of spontaneous recovery over the period of observation to be 20%. Of note, the clinical photographs showing regrowth indicate relatively limited regrowth limited to small patches at injection sites. Side effects noted were minimal and included: hemorrhage at injection sites, easily controlled with pressure, minimal atrophy, and no incidence of “sepsis”. In one patient, plasma cortisol levels were monitored by 9am samples. The pretreatment level of 14.8 μ g/100ml was reduced to 2.7 μ g/100ml the day following a dosage of 22.5mg of triamcinolone acetonide. The resting level was regained by day 3 and remained normal over the next 10 days (8).

In general practice, a concentration of 5mg/ml of TAC with a maximum volume of 6ml (30mg total) or 10mg/ml of TAC with a maximum volume of 3ml can be used on the scalp in one visit. Multiple intradermal injections using a 30 gauge needle are administered approximately 1 cm apart with injection of approximately 0.1ml per site. Initial regrowth may be seen in 4 to 8 weeks (9), (10). Side effects include mild, transient skin atrophy, lasting 2 to 8 months especially if too great a volume is injected or if the injection is too superficial or too deep(11). Transient pain is an additional side effect which limits the use of this modality in some patients, especially children(4). Ironically, younger patients (children) have been reported to have comparatively better hair growth in response to intralesional steroids(9). Topical anesthetics may be used to decrease discomfort. If there is no regrowth after 6 months of treatment, therapy with intralesional steroids should be stopped(10).

Mechanism of action of intralesional steroids

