in which fewer than 10% are expected to achieve this magnitude of hair regrowth spontaneously. In contrast, clinical experience would suggest that approximately 50% of subjects treated with either dose of IL TAC may achieve $\geq 50\%$ improvement in SALT score after 6 months of treatment. The goal of this study is to validate or refute this clinical impression and to objectively and precisely quantify the treatment effect of 2.5mg/ml, 5mg/ml or 10mg/ml of IL TAC in AA.

Subjects will be randomized 1:1:1:1 to the placebo or treatment arms, and will receive 6 months of treatment with the study medication or placebo. IL TAC 2.5mg/ml, 5mg/ml, 10mg/ml or placebo will be administered at baseline, then every 4 weeks thereafter for 5 cycles (weeks 4, 8, 12, 16, 20) for a total treatment period of 6 months. Percent hair regrowth from baseline will be determined by SALT measurements following 4, 8, 12, 20 and 24 weeks of treatment. Punch biopsies and peripheral blood will be obtained at baseline prior to treatment, and then once again at a time point between weeks 4 and 20, to be determined by the investigator as indicated by clinical considerations such as variation in the timeline to regrowth from one subject to another, for immunomonitoring/biomarker studies. Additional, optional scalp biopsies and blood draws may be taken at other key time points in order to monitor response to therapy at the discretion of the investigator and with the consent of the study subject. Efficacy will be measured by change in hair re-growth as determined by physical exam and photography, as well as by patient and physician global evaluation scores. Physician and patient global evaluation scores will be determined based on the use of similar 100mm Visual Analogue scales with 0 labeled as no scalp hair loss and 100 labeled as complete scalp hair loss. Patients and physicians will place a vertical mark along the horizontal line depending on their assessment of the degree of hair loss present at the time of assessment.

As secondary endpoints, efficacy will be measured by changes in hair re-growth as a continuous variable as determined by physical exam, SALT score and Canfield photography, as well as patient and physician global evaluation scores.

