Power analysis is based on a chi-squared test of proportions of responders in the 4 study groups, where response is defined as 50% reduction in SALT score. Effect size is quantified in terms of Cohen's w , a function of the response rates in the fourgroups (15). A minimal treatment effect size of 40% (Cohen's $w = 0.4$) i.e. a 50% response rate for active drug (IL TAC 2.5mg/ml, 5mg/ml or 10mg/ml) versus a presumed spontaneous remission response rate of 10% for patients receiving inactive IL saline, would be considered clinically meaningful in this study. To achieve 80% power to detect the desired effect size of 40% with a usual 5% level of significance (alpha), we would require approximately 17 subjects per arm (68 subjects in total). With this sample size, an effect size of 50% (Cohen's $w = 0.5$, "large" effect) would ensure approximately 95% power. Our postulated effect size for IL TAC is based on impressions due to clinical use of IL TAC in AA, however an explicit aim of this pilot study is to objectively and more precisely quantify the actual treatment effect of the various doses of IL TAC versus saline placebo.

Data Analysis Plan

The primary analysis will be a comparison of response rates in the 4 study groups, using a chi-squared test of proportions. If the 4-group comparison is significant, we will compare the efficacy and safety profiles of the three doses of intralesional triamcinolone head to head. For secondary outcomes that are binary (response/non-response), we will follow the same strategy. For secondary outcomes that are continuous (e.g. change in SALT measurement or PGA), we will conduct 4-group ANOVA tests, followed by pairwise

comparisons, if necessary. In both cases, Bonferroni correction will be made to adjust for multiple testing. To assess safety, we will summarize and test the incidence rates of adverse events across groups.

If possible, we will attempt to stratify the patients based on baseline degree of hair loss e.g. 0-25% vs. 26-50% hair loss in order to assess if response is correlated with degree of hair loss present at baseline. (Olsen E. Investigative guidelines for alopecia areata.

Dermatologic therapy 24, 2011 311-319

All outcomes will be analyzed on the intent to treat (ITT) basis.

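### The stated 80% power is about 76% at the plan's own 10% and 50% rates, and it depends heavily on a saline response rate that has no stated source

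*Combined protocol and SAP*

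**What the plan says.** All references are to the combined protocol and SAP.

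- **Sample size.** "Power analysis is based on a chi-squared test of proportions of responders in the 4 study groups". The target is "A minimal treatment effect size of 40% (Cohen's $w = 0.4$) i.e. a 50% response rate for active drug", set against "a presumed spontaneous remission response rate of 10% for patients receiving inactive IL saline". From this the section derives 17 per arm (68 in total) for 80% power at the 5% level, and about 95% power at w = 0.5. It bases the postulated effect on impressions from clinical use. It gives no source for the 10% and shows no other saline rate.
- **Methods, Specific Aim 1; Assessment of efficacy; Study outcomes.** All three use 10% as an upper limit for the control arm, "in which fewer than 10% are expected to achieve this magnitude of hair regrowth spontaneously", where the magnitude is at least 50% regrowth by SALT at week 24. The support offered is that the definition is strict. The last two sections cite two earlier trials for the choice of endpoint but report no control rate from them.
- **Clinical experience with IL TAC for AA.** This section describes an earlier study of triamcinolone 5 mg/ml with examinations at 6 and 12 weeks, in which 15 patients were injected with saline. "Seven percent of patients treated with saline had regrowth at 12 weeks", while "the authors attributed the incidence of spontaneous recovery over the period of observation to be 20" per cent. Neither figure is mentioned again in the sizing.

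**The concern.** Two things look wrong. First, the plan treats a 40-point difference in response and w = 0.4 as the same quantity, so the 80% may not belong to the 10% and 50% rates beside it. Second, the saline rate is presumed in one section and treated as a ceiling in three others. Yet the protocol's own background reports one control figure below 10% and one at twice 10%, and discusses neither.

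At stake is what a non-significant four-group test would mean. The Methods section says "The goal of this study is to validate or refute this clinical impression". A reader relying on 80% power would take a null result as fairly strong evidence against the treatment. If the saline rate were well above 10% and active response were 50%, that reading would be unsafe.

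**Working it through.** **Inputs.** Four equal arms of 17 (N = 68), Pearson chi-squared test with 3 df, alpha 0.05 (critical value 7.815), active response 50% in each dose arm and saline 10% (Sample size). Alternative saline rates of 7% and 20% come from the background section. 15% is an intermediate value chosen here. No dropout allowance is stated and none is applied.

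**Formulas.** With p̄ the mean of the four rates, w = √[mean of (pᵢ − p̄)² ÷ p̄(1 − p̄)]. Approximate power is the probability that a noncentral chi-squared variable with 3 df and λ = N·w² exceeds 7.815. As a check, binomial counts of 17 per arm were simulated 400,000 times and the Pearson test applied to each set.

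**Step 1: the plan's own figures.** At w = 0.4, λ = 68 × 0.16 = 10.88 and power is 79.9% (69 patients for 80%). At w = 0.5, power is 94.8%. Both stated powers reproduce, so they are powers for those values of w.

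**Step 2: the plan's own rates.** For 10/50/50/50%, p̄ = 0.40 and the mean squared deviation is (0.09 + 3 × 0.01) ÷ 4 = 0.03. Then w² = 0.03 ÷ 0.24 = 0.125 and w = 0.354, not 0.4. With λ = 8.5, approximate power is 68.4% and simulated power 75.9%. The simulation is the better guide here: the approximation uses the pooled variance 0.24 in every arm, while the saline arm at 10% has variance 0.09.

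**Step 3: vary the saline rate.**

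| Saline | Active (all doses) | w | Power, simulated | Power, noncentral |
|---|---|---|---|---|
| 7% | 50% | 0.381 | 85% | 76% |
| 10% | 50% | 0.354 | 76% | 68% |
| 15% | 50% | 0.308 | 59% | 55% |
| 20% | 50% | 0.263 | 43% | 42% |
| 20% | 60% | 0.346 | 70% | 66% |
| 20% | 71% | 0.448 | 92% | 89% |

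The 60% row keeps the 40-point difference. The 71% row uses the earlier study's 12-week response in limited disease.

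**Step 4: what the control figures can bear.** If all 15 saline patients were evaluated (an assumption), 7% is 1 of 15, with exact 95% confidence interval 0.2% to 32%. That excludes neither 10% nor 20%. The 20% is an estimate attributed to that study's authors. Its period is not given in weeks, and the last examination described is at 12 weeks.

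**The case against.** The case for the plan is substantial.

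- **The observed saline rate agrees with 10%.** Taken as it stands, 7% raises simulated power to 85%. This stands, and any range shown must include it.
- **The endpoint and population differ.** The earlier study counted pigmented terminal hair at injection sites, in an amount it did not define, and included patients up to alopecia universalis. This trial requires a 50% fall in SALT and excludes patients with regrowth under way at baseline. Both could lower the control rate, while reading at week 24 instead of week 12 could raise it. The documents quantify none of this. So 20% cannot be called the right rate, and 10% cannot be called optimistic.
- **20% against 50% is a 30-point difference.** The plan names 40 points as its minimal meaningful effect. With 40 points kept, power is about 70%, roughly 6 points below the 76% at the plan's rates. This stands.
- **The 43% case mixes sources.** It pairs that study's control estimate with an active rate drawn from clinical impression. The study's own 71% against 20% gives about 92%. This also stands, although 50% is the active rate on which the plan is sized.
- **The plan admits the uncertainty.** It calls the rate presumed, calls the trial a pilot, and makes estimation of the effect an explicit aim. This lessens the harm but does not correct the 80%.

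Two stronger readings are tempting. One is that the saline rate alone takes power from 80% to 43%. It does not: the 80% belongs to w = 0.4, and the saline effect is a fall from about 76% to about 43%. The other is to carry 7% forward at a constant rate to week 24, 1 − 0.93² = 13.5%, and conclude that the ceiling is already breached. That figure is not in the documents. It rests on about one patient, and it treats response status at a visit as cumulative incidence although the protocol itself provides for relapse.

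**Conclusion.** The point holds in limited form. The 80% is not delivered at the rates printed beside it: power there is about 76% by simulation, or 68% by the noncentral approximation. The 10% is unsourced, and the only control figures in the documents lie on both sides of it. With active response at 50% in all three doses, simulated power ranges from about 85% at 7% saline to about 43% at 20%. If the 40-point difference is kept at 20% saline, it is about 70%.

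These figures assume equal response across the doses, 17 analysed per arm and no dropout. They show sensitivity to an uncertain input. They do not show that the saline rate will be 20%, or that the trial is too small.

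**What to change.** 1. **Sample size.** Replace the single 80% statement with power by saline rate for the four-group test at 17 per arm. With active response at 50%: about 85% at 7%, 76% at 10%, 59% at 15% and 43% at 20%. Add the fixed 40-point case, 20% against 60%: about 70%. State that these are simulated values.
2. **Same section.** Cite the earlier study for the 7% and the 20%. Note that 15 patients were injected with saline, that the 20% is its authors' estimate, that the horizon is about 12 weeks, and that the endpoint is not SALT-based.
3. **Methods (Specific Aim 1), Assessment of efficacy and Study outcomes.** Describe 10% as an assumption rather than a ceiling. Do not insert the 20% there: those sentences concern 50% regrowth by SALT, which the earlier study did not measure.

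The cost is wording, and a less favourable stated power at the plan's own rates. No patients, visits, procedures or changes to the test are needed.

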S: Scalp hair loss

  S0 = No hair loss	  S4 = 76%-99% hair loss
  S1 = less than or equal to 25% hair loss	  a = 76%-95% hair loss
  S2 = 26%-50% hair loss	  b = 96%-99% hair loss
  S3 = 51%-75% hair loss	  S5 = 100% hair loss

Olsen/Canfield

FIG. 2. Olsen/Canfield tool for determination of %scalp hair loss. Percentages represent scalp surface area (reprinted with permission).

[figure not shown]

Figure 9. SALT score.

The percentage of hair loss in any one of the four views (areas) of the scalp = the percentage hair loss x percent surface area of the scalp in that area. The SALT score then equals the sum of the scalp hair loss in each area.

- (a) Top (left side view) = $95\% \times .18 = 17.1$
- (b) Second (right side view) = $90\% \times .18 = 16.2$
- (c) Third (top of scalp) = $95\% \times .40 = 38$ (realizing that most of hair loss is probably male pattern hair loss)
- (d) Bottom (back of scalp) = $55\% \times .24 = 13.2$

$a+b+c+d = 17.1 + 38 + 16.2 + 13.2 = 84.5\% \text{ hair loss or SALT } 84.5$

Body hair loss

B0 = No body hair loss

B1 = some body hair loss

B2 = total (100%) body hair loss

Nail involvement

N0 = No nail involvement

N1 = some nail dystrophy

N1a = 20 nail dystrophy

Percentage change from baseline (% regrowth) =

$[(SALT \text{ BL} - SALT \text{ F/U}) / SALT \text{ BL}] \times 100\% = \% \text{ change from baseline}$

Absolute regrowth = SALT BL – SALT F/U = absolute change from BL

Study outcomes

Primary efficacy outcome:

1. Comparison of the proportion of responders in each group, with response defined as 50% change (% change NOT absolute change) in SALT score from baseline (50% regrowth at week 24).

This is a relatively strict definition for defining responders and non-responders and was chosen based on consensus of clinicians and AA experts that 50% reduction in SALT score represents clinically meaningful response and to minimize responses in the “vehicle” arm, in which fewer than 10% are expected to achieve this magnitude of hair regrowth spontaneously. This outcome was also used in two recent RCT trials (Strober et al. 2009 and Price et al. 2008) evaluating therapies for AA.

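### The Sample size section treats a 40-point difference as Cohen's w = 0.4; the stated rates give w = 0.354, and 68 patients give about 76% power, not 80%

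*Combined protocol and SAP*

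**What the plan says.** The Sample size section names the test: "Power analysis is based on a chi-squared test of proportions of responders in the 4 study groups". It describes Cohen's w as a function of the four response rates. It then gives the target effect as "A minimal treatment effect size of 40% (Cohen's $w = 0.4$) i.e. a 50% response rate for active drug" (any of the three IL TAC strengths) "versus a presumed spontaneous remission response rate of 10% for patients receiving inactive IL saline". The goal is set as follows: "To achieve 80% power to detect the desired effect size of 40% with a usual 5% level of significance (alpha"). The number of patients derived from that goal reads: "we would require approximately 17 subjects per arm (68 subjects in total").

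A second figure follows the same pattern. An effect size of 50%, written as w = 0.5, "would ensure approximately 95% power". No response rates are given for that figure.

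The Data Analysis Plan makes the same 4-group chi-squared test the primary analysis. The Methods text under Specific Aim 1 sets 1:1:1:1 allocation and expects about 50% response on IL TAC. For the saline arm, the Methods text, Assessment of efficacy and Study outcomes each describe a group "in which fewer than 10% are expected to achieve this magnitude of hair regrowth spontaneously".

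**The concern.** The text pairs 40% with w = 0.4 and 50% with w = 0.5. That is what results when a difference in response rates is entered where w belongs. For a table of four groups by two outcomes, w depends on how far each arm lies from the overall rate and on that overall rate, so the two quantities need not agree.

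This paragraph is the only justification for 68 patients. The Methods text says of the expected 50% response: "The goal of this study is to validate or refute this clinical impression". A reader of a non-significant result needs the true probability of missing that effect. Anyone who reused the rule that 40 points means w = 0.4 would undersize another trial with the same 10/50/50/50 pattern.

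**Working it through.** **Inputs.** Four equal arms of 17, N = 68; Pearson chi-squared test with 3 degrees of freedom; alpha 0.05, critical value 7.815; saline 10%, active 50% (Sample size). All three doses are taken at 50%, the natural reading of that section and of the Methods text.

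**Step 1: reproduce the plan's figures.** Power = P(noncentral chi-squared, 3 df, noncentrality N × w² > 7.815).

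- w = 0.4: noncentrality 68 × 0.16 = 10.88, power 79.9%.
- w = 0.5: noncentrality 68 × 0.25 = 17.0, power 94.8%.

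These are the stated 80% and 95%, so the calculation evidently started from w = 0.4 and w = 0.5.

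**Step 2: compute w from the stated rates.** For equal arms, w² = mean of (p_i − p̄)² divided by p̄(1 − p̄).

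- p̄ = (0.10 + 3 × 0.50)/4 = 0.40.
- w² = [0.25 × (0.30² + 3 × 0.10²)]/(0.40 × 0.60) = 0.03/0.24 = 0.125.
- w = 0.354, not 0.4.

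With saline at 10%, w = 0.4 needs about 55.9% on every dose, and w = 0.5 about 67.6%.

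**Step 3: power at the stated rates with 68 patients.**

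- Plan's apparent formula: noncentrality 68 × 0.125 = 8.5, power 68.4%.
- Exact: binomial probabilities summed over all 18⁴ = 104,976 outcomes with the Pearson statistic above 7.815 give 75.9%. Simulation agrees (75.9%).

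The noncentral formula understates the power of the actual test here. The exact type I error is 4.6% with all arms at 10% and 5.0% with all arms at 40%, so the higher exact power does not come from an inflated test.

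**Step 4: the second figure.** If the 50% effect size means 60% against 10% (an inference, since the plan gives no rates), p̄ = 0.475, w² = 0.046875/0.249375 = 0.188 and w = 0.434. Power is 93.2% exact, or 86.5% by the formula, against the stated 95%.

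**Step 5: arm size and saline rate.** At 10% and 50%, exact power is 79.0% with 18 per arm and 80.9% with 19 per arm (76 patients). By the plan's formula, 22 per arm (88 patients) are needed for 80.4%.

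With 17 per arm and 50% on every dose:

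| Saline rate | Exact power |
|---|---|
| 10% | 75.9% |
| 9% | 79.2% |
| 8% | 82.3% |
| 7% | 85.3% |
| 5% | 90.8% |

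Exact power reaches 80% at a saline rate of about 8.7%.

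**The case against.** The strongest reply is that the shortfall lies within the plan's own uncertainty. Elsewhere the protocol expects fewer than 10% on saline and only approximately 50% on active drug. Exact power reaches 80% at 8.7% on saline or, with saline at 10%, at 51.8% on active. At 5% and 50%, w is in fact 0.400. It follows that 68 patients is not clearly too few. It does not make the equation right: the Sample size section fixes saline at 10%, and its parallel pairing of 50% with w = 0.5 points to a substitution, not to a 5% assumption.

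The dose pattern is also an assumption. If two doses respond at 50% and the third at 10%, w = 0.436 and exact power is 90.0%. If only one responds, w = 0.433 and exact power is 84.5%. A graded pattern of 10/30/50/50 lowers exact power to 71.0%. A two-group comparison of 50% with 10% gives w = 0.436. None of the readings with responding doses at 50% and the rest at 10% gives 0.4.

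Three further points stand. The 60% scenario is inferred, and 93% is close to approximately 95%. Comparing 76% with 80% sets an exact figure against an approximation; the like-for-like figure is 68.4%. And the plan calls the trial a pilot that aims to quantify the effect, which lowers the stakes.

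**Conclusion.** The concern holds. The stated w is wrong for the stated rates (0.354, not 0.4), and the planned test with 68 patients has 75.9% exact power at those rates, not 80%. The probability of missing the effect is 24.1% instead of 20%. This rests on 10% on saline, 50% on each of the three doses, 17 patients per arm, and a known outcome for all 68; the sample size text makes no allowance for dropout. The error in the text is certain and its practical size is modest. It should be corrected because a power figure the trial relies on cannot be obtained from the rates given beside it.

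**What to change.** In the Sample size section, remove the equation of w with a percentage-point difference, name the method and state the rates. For example:

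> With 17 subjects per arm (68 in total), the 4-group Pearson chi-squared test at the 5% level has about 76% power (exact calculation) if response rates are 10% on saline and 50% on each IL TAC dose (w = 0.354), and about 93% power if they are 10% and 60% (w = 0.434). If the saline rate is 8%, power for 50% on each dose is about 82%.

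The authors should confirm that 60% is what they meant by the larger effect, or drop that clause.

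The cost is the rewording of one paragraph. Sample size, conduct and analysis stay as they are. The stated power falls from 80% to about 76% and, on the 60% reading, from 95% to about 93%.
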